3. OBJECTIVES AND ENDPOINTS

Objectives	Endpoints
Primary	Primary

To describe the PK profiles of CAB 400 mg/mL formulation following multiple injections administered intramuscularly (gluteus medius or vastus lateralis) or subcutaneously (abdominal) in healthy adult participants
 
To assess the relative bioavailability of a CAB 400 mg/mL formulation administered via different routes (i.e., IM (vastus lateralis), IM (gluteus medius) or SC routes)
 
To compare exposures after CAB 400 mg/mL formulation administered via different routes with historical data of CAB 200 mg/mL formulation administered IM (gluteus medius)
	
Summary measures to include:
 
 • Maximum observed plasma concentration (C_{max}) [Injection 1 and 2] • Time of maximum observed plasma concentration (t_{max}) [Injection 1 and 2] • Area under the concentration – time curve for each injected dose from time zero to last quantifiable time point or 4 weeks following injection whichever is earlier (AUC_{0-t}) • Trough concentrations (C_τ) at 4 weeks following first injection (or earlier if the second injection occurs at <4-week interval) and 4 weeks following the second injection • Apparent terminal phase half-life (t_{1/2}) and absorption rate constant (K_{ALA}) [Injection 2] 
• Pair-wise comparisons of geometric mean ratios of plasma trough concentrations (C_τ), C_{max}, and Plasma AUC_{0-t} [injection phase] for Cohort 1, 2, 3, 4, 4b, and 4h
 
• Geometric mean ratios of plasma trough concentrations (C_τ) for Cohorts 1, 2, 3, 4, 4b, 4h, 5, and 6 (if conducted) compared to historical CAB 200 mg/ml data

Objectives	Endpoints
Safety	Safety

To assess safety and tolerability of CAB 400 mg/mL formulations following repeated intramuscular injections in the gluteus medius, vastus lateralis (lateral thigh) or subcutaneously (abdomen) of healthy adult participants
 
To assess safety and tolerability of CAB 200 mg/mL with rHuPH20 following a subcutaneous (abdominal) injection in healthy adult participants
 
To assess safety and tolerability of CAB 400 mg/mL with rHuPH20 following a subcutaneous (abdominal) injection in healthy adult participants
	
Safety and tolerability parameters including adverse events, clinical laboratory tests, and vital sign assessments

Secondary	Secondary

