11.9. Appendix 9: Abbreviations and Trademarks

AC	Active control
ADA	Anti-drug antibody
AE	Adverse event
ALT	Alanine aminotransferase (SGPT)
AST	Aspartate aminotransferase (SGOT)
AUC	Area under concentration-time curve
AUC0-t	Area under the concentration-time curve for each injected dose from time zero to last quantifiable time point
AUC(0-24)	Area under the concentration-time curve over 24 hours
AV	Atrioventricular
hCG	Human Chorionic Gonadotropin
BMI	Body mass index
BUN	Blood urea nitrogen
C24	Concentration at 24 hours
CAB	Cabotegravir
CI	Confidence interval
CIOMS	Council for International Organizations of Medical Sciences
C _{max}	Maximum observed concentration
C _{min}	Minimum observed concentration
C _τ	Last observed quantifiable concentration
CONSORT	Consolidated Standards of Reporting Trials
CPK	Creatine phosphokinase
CPMS	Clinical Pharmacokinetics Modelling & Simulation
CRF	Case Report Form
CV	Coefficient of variance
DDI	Drug-drug interaction
DILI	Drug Induced Liver Injury
DNA	Deoxyribonucleic acid
DTG	Dolutegravir
ECG	Electrocardiogram
EDP	ENHANZE™ Drug Product
EW	Early withdrawal
FDA	Food and Drug Administration
FPFV	First participant First Visit
FRP	Females of reproductive potential
FSH	Follicle Stimulating Hormone
GCP	Good Clinical Practice
GCSP	Global Clinical Safety and Pharmacovigilance
GLP	Good Laboratory Practice
GSK	GlaxoSmithKline
HBsAg	Hepatitis B surface antigen
hCG	Human chorionic gonadotropin
HCP	Healthcare provider

HDPE	High density polyethylene
HIV	Human Immunodeficiency Virus
HRT	Hormonal replacement therapy
HSR	Hypersensitivity Reactions
IB	Investigator's Brochure
ICF	Informed consent form
ICH	International Conference on Harmonization of Technical Requirements for Registration of Pharmaceuticals for Human Use
IDMC	Independent Data Monitoring Committee
IDSL	Integrated Data Standards Library
IEC	Independent Ethics Committee
IM	Intramuscular
IMP	Investigational Medicinal Product
IND	Investigational New Drug
INR	International normalized ratio
IP	Investigational Product
IRB	Institutional Review Board
IRT	Interactive response technology
ISRs	Injection Site Reactions
IUD	Intrauterine device
IUS	Intrauterine hormone-releasing system
λ_z	Terminal phase rate constant
L	Liter
LA	Long Acting
LAM	Lactational amenorrhoea method
LAP	Long acting parenteral
LFTs	Liver function tests
μg	Microgram
μL	Microliter
MCH	Mean corpuscular hemoglobin
MCHC	Mean corpuscular hemoglobin concentration
MCV	Mean corpuscular volume

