2. SUMMARY OF KEY PROTOCOL INFORMATION

2.1. Changes to the Protocol Defined Statistical Analysis Plan

There were no changes or deviations to the originally planned statistical analysis specified through protocol amendment 6.

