2.2. Study Objective(s) and Estimand(s) / Endpoint(s)

Objectives	Estimands / Endpoints
Primary	Primary
PK	PK

 To describe the pharmacokinetic (PK) profiles of CAB 400 mg/mL formulation following multiple injections administered intramuscularly (gluteus medius or vastus lateralis) or subcutaneously (abdominal) in healthy adult participants) 	
 Maximum observed plasma concentration (C_{max}) [Injection 1 and 2] Time of maximum observed plasma concentration (t_{max}) [Injection 1 and 2] Area under the concentration – time curve (AUC) for each injected dose from time zero to last quantifiable time point or 4 weeks following injection whichever is earlier (AUC_{0-t}) Trough concentrations (C_τ) at 4 weeks following first injection (or earlier if the second injection occurs at <4-week interval) and 4 weeks following the second injection Apparent terminal phase half-life (t_{1/2}) and absorption rate constant (K_{ALA}) [Injection 2]

 To assess the relative bioavailability of a CAB 400 mg/mL formulation administered via different routes (i.e., IM (vastus lateralis), IM (gluteus medius) or SC routes) To compare exposures after CAB 400 mg/mL formulation administered via different routes with historical data of CAB 200 mg/mL formulation administered IM (gluteus medius) 	
Pair-wise comparisons of geometric mean ratios of plasma trough concentrations (C_T), C_{max}, and AUC_{0-t} [injection phase] for Cohorts 1, 2, 3, 4, 4b, and 4h
 
Geometric mean ratios of plasma trough concentrations (C_T) for Cohorts 1, 2, 3, 4, 4b, 4h, 5, and 6 (if conducted) compared to historical CAB 200 mg/mL data

Safety	Safety

 To assess safety and tolerability of CAB 400 mg/mL formulations following repeated intramuscular injections in the gluteus medius, vastus lateralis (lateral thigh) or subcutaneously (abdomen) of healthy adult participants. To assess safety and tolerability of CAB 200 mg/mL with rHuPH20 following a subcutaneous (abdominal) injection in healthy adult participants. To assess safety and tolerability of CAB 400 mg/mL with rHuPH20 following a subcutaneous (abdominal) injection in healthy adult participants. 	
 Safety and tolerability parameters including adverse events (AEs), clinical laboratory tests, and vital sign assessments.
Secondary	Secondary
Safety	Safety

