8.1.1.2. Derived Pharmacokinetic Parameters

Pharmacokinetic parameters will be calculated by standard non-compartmental analysis according to current working practices and using the currently supported version of WinNonlin (8.0 or higher). All calculations of non-compartmental parameters will be based on actual sampling times. Pharmacokinetic parameters listed will be determined from the plasma concentration-time data from OLI and Injection phases, as data permit.

Parameter	Parameter Description	OLI Phase	Injection Phase
C _{max}	Maximum observed plasma concentration determined directly from the concentration-time data.	Day 1	For Injection 1 and 2 in Part 1 and Part 2
C _{max} /D	Dose normalized C _{max} , calculated as C _{max} /Dose	Day 1	For Injection 1 and 2 in Part 1 and Part 2
t _{max}	Time of C _{max} determined directly from the concentration-time data.	Day 1	For Injection 1 and 2 in Part 1 and Part 2
AUC(0-t)	Area under the concentration time curve from time zero to last quantifiable time point calculated using the linear trapezoidal rule for each incremental trapezoid and the log trapezoidal rule for each decremental trapezoid.	Day 1	For Injection 1 & 2 in Part 1 and Part 2
AUC(0-t)/D	Dose normalized AUC(0-t), calculated as AUC(0-t)/Dose	Day 1	For Injection 1 & 2 in Part 1 and Part 2
AUC(0-τ)	Area under the concentration time curve from time zero to tau time point calculated using the linear trapezoidal rule for each incremental trapezoid and the log trapezoidal rule for each decremental trapezoid. Tau=24 hours for OLI Day 1 Tau is 4 weeks for Cohort 1-4, 4b and 4h Tau is 12 weeks for cohort 5	Day 1	For Injection 1 & 2 in Part 1 and Part 2
AUC(0-τ)/D	Dose normalized AUC(0-τ) calculated as AUC(0-τ)/Dose	Day 1	For Injection 1 & 2 in Part 1 and Part 2

Parameter	Parameter Description	OLI Phase	Injection Phase
AUC(0-4) Cohort 5 only	Area under the concentration time curve from time zero to Week 4 calculated using the linear trapezoidal rule for each incremental trapezoid and the log trapezoidal rule for each decremental trapezoid.	NA	Injection 1 Part 2 (Cohort 5) (this parameter is used in the dose proportionality analysis).
AUC(0-∞)	Area under the concentration time curve from time zero to infinity	NA	For Injection 1 (Cohort 4h) & 2 in Part 1 and Part 2
AUC(0-∞)/D	Dose normalized AUC(0-∞), calculated as AUC(0-∞)/Dose	NA	For Injection 1 (Cohort 4h) & 2 in Part 1 and Part 2

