Injection 1	a) Injection 1 Day 1 Pre-dose Samples: Start Date & Time < Date & Time of First CAB Injection b) All Other Samples: For participants receiving second CAB injection: Date & Time of First CAB Injection ≤ Start Date & Time < Date & Time of Second CAB Injection For participants not receiving second CAB injection: Date & Time of First CAB Injection ≤ Date & Time and Start Date ≤ Date of Nominal Follow-up Week 4/Day 28 Visit [for Part 1 participants] / Nominal Follow-up Week 12 Visit [For Part 2 participants]
Injection 2	Date & Time of Second CAB Injection ≤ Date & Time and Start Date ≤ Date of Nominal Follow-up Week 4/Day 28 Visit [for Part 1 participants] / Nominal Follow-up Week 12 [for Part 2 Participants]
Follow-up	Start Date > Date of Nominal Follow-up Week 4/Day 28 Visit [for Part 1 participants] / Nominal Follow-up Week 12 Visit [for Part 2 participants]
Injection 2 Day 1 Pre-dose Samples: The original record will be assigned to Period = Injection 1 (as defined above). A duplicate record will be created and assigned to Period = Injection 2.	

Follow-up Week 4 [for Part 1 Participants], Follow-up Week 12 [for Part 2 Participants] Samples: If participant is not receiving second injection, the original record will be assigned to Period = Injection 1 (as defined above). A duplicate record will be created and assigned to Period = Follow-up. If participant has received second injection, the original record will be assigned to Period = Injection 2 (as defined above). A duplicate record will be created and assigned to Period = Follow-up.	
For Other Assessments (Excluding AEs and PK)	
Study Period	Date range
Screen	If actual "Time of Day" for the assessment/event is collected: Date & Time < OLI Treatment Start Date & Time If actual "Time of Day" for the assessment/event is not collected: Date < OLI Treatment Start Date
OLI	If actual "Time of Day" for the assessment/event is collected: For participants continuing into Injection Phase: OLI Treatment Start Date & Time ≤ Date & Time < Date & Time of First CAB Injection For participants not continuing into Injection Phase: Date & Time ≥ OLI Treatment Start Date & Time If actual "Time of Day" for the assessment/event is not collected: For participants continuing into Injection Phase: OLI Treatment Start Date ≤ Date < Date of First CAB Injection For participants not continuing into Injection Phase: Date ≥ OLI Treatment Start Date

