10.9. Appendix 9: Abbreviations & Trademarks

10.9.1. Abbreviations

Abbreviation	Description
AC	Active Control
ADaM	Analysis Data Model
AE	Adverse Event
ANOVA	Analysis of Variance
AUC	Area under Concentration-Time Curve
AUC0-t	AUC for each Injected Dose from Time Zero to Last Quantifiable Time Point or 4 Weeks Following the Injection, whichever is earlier
BMI	Body Mass Index
CAB	Cabotegravir
CDISC	Clinical Data Interchange Standards Consortium
CI	Confidence Interval
C _{max}	Maximum Observed Plasma Concentration
CSR	Clinical Study Report
C _τ	Trough Concentrations at 4 Weeks Following First Injection (or Earlier If The Second Injection Occurs at <4-Week Interval) and 4 Weeks Following The Second Injection
DBF	Database Freeze
DBR	Database Release
DP	Decimal Place
DVM	Data Validation Manual
eCRF	Electronic Case Report Form
CV	Coefficient of Variation
CV _b	Between-Subject Geometric CV
ECG	Electrocardiogram
GSK	GlaxoSmithKline
IA	Interim Analysis
ICF	Informed Consent Form
IDSL	Integrated Data Standards Library
IG	Implementation Guide
IM	Intramuscular
ISR	Injection Site Reaction
K _{ALA}	Terminal Absorption Elimination Rate Constant
LLN	Lower Limit of Normal
NQ	Not Quantifiable Value
CCI	
OLI	Oral Lead-In
CCI	
PK	Pharmacokinetic
Q4W	Four-Weekly

Q12W	Twelve-Weekly
QD	Once Daily
QTcB	QT Duration Corrected for Heart Rate by Bazett's Formula
QTcF	QT Duration Corrected for Heart Rate by Fridericia's Formula
RAP	Reporting and Analysis Plan
REML	Restricted Maximum Likelihood
SAC	Statistical Analysis Complete
SAE	Serious Adverse Event
SAS	Statistical Analysis Software
SC	Subcutaneous
SD	Standard Deviation
SDL	Source Database Lock
SDTM	Study Data Tabulation Model
SMQ	Standardized MedDRA Query
SRT	Safety Review Team
STR	Study Team safety & PK Review
$t_{1/2}$	Terminal Absorption Elimination Half-Life
tmax	Time of Cmax
ULN	Upper Limit of Normal

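### SAP 8.1.1.2 derives AUC(0-t) and AUC(0-t)/D without the 4-week limit that defines this primary endpoint elsewhere, so Cohort 5's descriptive values would cover 12 weeks against about 4 in Part 1

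*SAP*

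**What the plan says.** **With the 4-week limit.** Protocol section 3 defines the primary endpoint AUC0-t as the area "from time zero to last quantifiable time point or 4 weeks following injection whichever is earlier", with no exception for the 12-weekly cohorts. SAP 2.2 repeats it: "time zero to last quantifiable time point or 4 weeks following injection whichever is earlier". SAP 10.9.1 does too: "AUC for each Injected Dose from Time Zero to Last Quantifiable Time Point or 4 Weeks Following the Injection, whichever is earlier".

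**Without the limit.** The derivation table in SAP 8.1.1.2 is what an analyst would program. It gives AUC(0-t) as "Area under the concentration time curve from time zero to last quantifiable time point calculated using the linear trapezoidal rule", for both injections in both parts. AUC(0-t)/D is that value divided by dose. The protocol's own abbreviation list (11.9) also has no limit: "Area under the concentration-time curve for each injected dose from time zero to last quantifiable time point". Nor does the gloss on AUC0-t in the synopsis rationale.

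**Data that enter.** SAP 8.1.1.2 states: "Pharmacokinetic parameters listed will be determined from the plasma concentration-time data from OLI and Injection phases". For PK data, SAP 10.4.1 Table 5 closes the Injection 1 period of a participant without a second injection at the Follow-up Week 4 visit in Part 1, and at the "Nominal Follow-up Week 12 Visit [For Part 2 participants"] in Part 2. SAP 2.3 records the decision that Cohort 5 would not receive Injection 2.

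**Related parameters.** SAP 8.1.1.2 also lists AUC(0-τ), with tau of 4 weeks in Part 1 and 12 weeks in Cohort 5, and an AUC(0-4) for Cohort 5 Injection 1 that is used for dose proportionality. It lists no AUC(0-4)/D.

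**Declared changes.** SAP 2.1 says: "There were no changes or deviations to the originally planned statistical analysis specified through protocol amendment 6".

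**The concern.** One primary endpoint has two definitions inside the SAP. An analyst who follows 8.1.1.2 and a reader who follows 2.2 or 10.9.1 would expect different Cohort 5 numbers under the same label.

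For Part 1 the two definitions nearly coincide, because the injection periods end at about 4 weeks. For Cohort 5 they do not. Its AUC(0-t) would run to Week 12 and nearly duplicate its AUC(0-τ), and the row carrying the primary endpoint's name would not hold the quantity defined in the endpoint tables.

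The dose-normalised version matters most for a reader. Cohort 1 (600 mg) and Cohort 5 (800 mg) are both gluteal. If exposure were exactly dose-proportional, AUC(0-t)/D would still look higher in Cohort 5, purely because of the integration limit. Both dose-normalised areas listed for Cohort 5 Injection 1, AUC(0-t)/D and AUC(0-τ)/D, span 12 weeks. AUC(0-∞)/D is listed for Injection 1 only in Cohort 4h. No 4-week area per mg is listed for Cohort 5.

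**Working it through.** **Step 1. Which window applies.**

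| | Part 1 | Cohort 5, Injection 1 |
|---|---|---|
| End of PK period (SAP Table 5) | second injection or Week 4 visit | Week 12 visit |
| AUC(0-t) by SAP 2.2 and 10.9.1 | up to 4 weeks | up to 4 weeks |
| AUC(0-t) by SAP 8.1.1.2 | about 4 weeks | up to 12 weeks, if quantifiable |

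**Step 2. Inputs for the size.** The documents give no ratio of 12-week to 4-week area. The usable figures are in Protocol 10.2 Table 3, for a simulated single 1200 mg dose with N = 16: Week 12 log mean 0.0311, SD 0.59603; Week 24 log mean -1.3837, SD 1.11507.

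**Step 3. Reproduce Table 3.** The formula is exp(mean ± t(0.95, 15) × SD/√16).
- Week 12: 1.0316 (0.7944, 1.3395), as printed.
- Week 24: 0.2506 (0.1538, 0.4086). The printed geometric mean is 0.2507, so they agree to rounding.

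**Step 4. Rate of decline.** k = ln(1.0316/0.2507)/12 = 0.118 per week, a half-life of ln 2/k = 5.88 weeks.

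**Step 5. Ratio of areas.**
- Mono-exponential: (1 - e^(-12k))/(1 - e^(-4k)) = 0.757/0.376 = 2.01.
- One-compartment curve with slow absorption at rate ka = k and elimination rate ke: A(T) = (1 - e^(-ka·T))/ka - (1 - e^(-ke·T))/ke, ratio A(12)/A(4). Protocol 4.2.1 equates the 7 to 14 day washout with about 5 to 9 half-lives, so the oral half-life is 7/5 = 1.4 to 14/9 = 1.56 days. The ratio is 2.11 to 2.13.

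**Step 6. Cross-check.** Double the Week 4 value that Table 3 assumes for 600 mg (2 × 1.3898 = 2.7796) and let it fall to the 1200 mg Week 12 value. Then k = ln(2.7796/1.0316)/8 = 0.124 per week, a half-life of 5.6 weeks. The ratio is 1.98 mono-exponential and 2.08 to 2.09 with absorption.

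**Step 7. Sensitivity to an assumed half-life** (absorption model with an oral half-life of 1.5 days).

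| Half-life (weeks) | Mono-exponential | With absorption |
|---|---|---|
| 2 | 1.31 | 1.37 |
| 4 | 1.75 | 1.84 |
| 8 | 2.21 | 2.33 |
| 12 | 2.42 | 2.56 |

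**Step 8. Part 1.** With the same decline, a last sample at Day 31 gives 1.08 times the Day 28 area, and one at Day 25 gives 0.91 times. The early case is the same with or without the cap. The missing cap can therefore add about 8% at most.

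**Step 9. Where AUC(0-t) is used.**
- SAP 8.1.2 and 8.1.5.1 compare cohorts pairwise on AUC(0-τ), Cmax and Cτ, and the comparisons in SAP 5.1 leave Cohort 5 out.
- Historical comparisons use Cτ.
- Dose proportionality sets AUC(0-τ) at 4 weeks for Part 1 against AUC(0-4) for Cohort 5.
- AUC(0-t) is left to the descriptive Tables 3.3 and 3.4 (SAP 10.10.7) and Listing 40 (SAP 10.10.10).

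**The case against.** The strongest reply is that this is a wording slip with no effect on any planned model estimate. Much of that stands. The SAP keeps the limit in 2.2 and 10.9.1. AUC(0-4), which equals the capped area when concentrations are quantifiable through Week 4, is already derived for Cohort 5 and used where exposure is compared across doses.

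It can also be said that the protocol is not uniform, since its abbreviation list and synopsis rationale omit the cap, and that the cap looks written for the 4-weekly cohorts. The adjacent endpoint places Cτ at 4 weeks without exception, yet Protocol 10.4.2 uses Week 12 Cτ for Cohorts 5 and 6. This stands as a reason to state which window is meant, and is why the fix offers two routes. It does not remove the conflict, because nothing in the SAP identifies AUC(0-4) as the primary AUC0-t.

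Finally, AUC(0-τ)/D would keep a 4-week against 12-week contrast after either fix. That is true, but its definition states tau by cohort, so the reader can see the mismatch.

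Stronger inferences that the documents do not support:
- A reader might infer that the relative bioavailability or dose-proportionality results are distorted. They are not; those analyses do not use AUC(0-t).
- A reader might infer that Part 1 Injection 2 and Cohort 4h areas could run to Week 52. SAP 8.1.1.2 restricts derivation to the oral lead-in and injection phases, and Table 5 assigns later samples to Follow-up.
- A reader might take the two-fold figure as a stated result. It is an estimate.

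**Conclusion.** The inconsistency is real and limited. As written, the derivation rule yields a Cohort 5 AUC(0-t) and AUC(0-t)/D that are not the endpoint defined in the protocol's endpoint table, SAP 2.2 and SAP 10.9.1, and SAP 2.1 does not disclose the difference. The affected outputs are the descriptive Tables 3.3 and 3.4 and the parameter listing.

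Where Week 12 is quantifiable, the Cohort 5 value would be roughly 2 times the capped one, with a range of about 1.3 to 2.6. The size rests on linear kinetics, on simulated 1200 mg data although Cohort 5 received 800 mg, and on assumed half-lives of 2 to 12 weeks. The direction does not depend on those choices: extending the window from 4 to 12 weeks can only add area. In Part 1 the effect is one of last-sample timing only.

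It is worth correcting before tables are produced, because it concerns a named primary endpoint and the correction is short.

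**What to change.** Either of two edits resolves it.

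1. In SAP 8.1.1.2, cap injection-phase AUC(0-t) and AUC(0-t)/D at 4 weeks after injection for every cohort, matching 2.2 and 10.9.1, and report Cohort 5's 12-week area only as AUC(0-τ). Cohort 5's AUC(0-t) will then equal AUC(0-4) where Week 4 is quantifiable.
2. If the uncapped parameter is wanted, state in SAP 8.1.1.2 that AUC(0-4) is Cohort 5's protocol-defined AUC0-t, add an AUC(0-4)/D row, and declare the uncapped AUC(0-t) in SAP 2.1 as an additional parameter.

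The cost is one line for the first route and a few for the second, plus the matching programming specification. No new data or samples are needed, and no planned model changes.

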8.1.2. Summary Measure

For PK concentrations and PK parameters: arithmetic mean, 95% confidence interval (CI) of arithmetic mean, geometric mean, 95% CI of geometric mean, SD, SD of log data, between-subject geometric coefficient of variation (CV_b), median, minimum, maximum, and coefficient of variation (CV), as appropriate.

For pairwise comparisons of AUC(0-τ), C_{max}, and C_τ (CAB 400 mg/mL) between cohorts: geometric mean ratio and corresponding 90% CI.

For cross study comparisons of C_{τ} to historical CAB 200 mg/mL data: geometric mean ratio and corresponding 90% CI.

For dose proportionality assessments of $AUC(0-\tau)$ [$AUC(0-4)$ for Cohort 5], C_{max} , and C_{τ} [C_4 for Cohort 5] following injection 1 for CAB 400 mg/mL (across all cohorts in Part 1 and Part 2, excluding cohort 4h) for each route: mean slope estimated from the power model and the corresponding 90% CI.

8.1.3. Population of Interest

The primary PK analyses will be based on the PK population.

